6.1 Primary objective

- To assess the relative risk of myotoxic events associated with concomitant exposure of LCZ696 together with statins compared with statin exposure alone in patients with HF
- To assess the relative risk of hepatotoxic events associated with concomitant exposure of LCZ696 together with statins compared with statin exposure alone in patients with HF
- To assess the relative risk of acute pancreatitis associated with concomitant exposure of LCZ696 together with statins compared with statin exposure alone in patients with HF

7 Research methods

7.1 Study design

This will be a non-interventional, multi-database, post-authorization safety study (PASS) using a case-control design with secondary use of electronic healthcare data. The study will retrieve information from various European electronic healthcare databases, i.e. one each from the UK, the Netherlands (NL), Spain (ES), Italy (IT), and Denmark (DK). See [Section 7.4](#) for details on the data sources to be used for the study.

Cases will be identified from the study base, which are adults, have HF and statin exposure during follow-up, at least one year of valid data (i.e. at least one year of database history available for a patient, meaning the patient was registered in the database for at least one year), and have a safety event of interest (either myotoxicity, hepatotoxicity or acute pancreatitis) during follow-up. Control patients (without a recorded event of interest prior to the index date of the case) will be matched to cases based on age (at index date), sex (see [Section 7.2.2.4](#)), and index date (= calendar date). Exposure to LCZ696 and statins in cases and matched controls within a certain risk period prior to the index date (= date of safety event of interest) will be assessed. There will be three separate case-control analyses, one each for myotoxicity, hepatotoxicity, and acute pancreatitis.

A case-control analysis is an effective method to assess potential DDIs on a population-based, real-world level using electronic healthcare information, since we are interested in the relative risk. It is more efficient to assess concomitant drug use at one point in time (i.e. at the index date) over the risk period rather than the entire period of follow-up, especially in this population that uses many different types of drugs. This type of design has been applied many times for assessing various different DDIs on a population-level using electronic healthcare databases (e.g. [Cressman et al 2015](#), [Pincus et al 2012](#), [Jobski, Behr and Garbe 2011](#), [Juurlink et al 2011](#), [Schelleman et al 2011](#), [Juurlink et al 2009](#), [Schelleman et al 2008](#)).

7.2 Setting

7.2.1 Source population

The source population for this study will be based on enrollees from five EU electronic healthcare databases, namely the ‘Sistema d’Informació per al Desenvolupament de la Investigació en Atenció Primària’ (SIDIAP) from Spain, the ‘PHARMO Database Network’ (PHARMO) from the Netherlands, the ‘Health Search CSD Longitudinal Patient Database’ (HSD) from Italy, the ‘Aarhus University Prescription Database’ from Denmark, and the UK ‘Clinical Practice Research Datalink’ (CPRD). Additional databases may be added if needed (e.g. from Germany). For details on the databases, see [Section 7.4](#) ‘Data sources’.

7.2.2 Study population

7.2.2.1 Study base

The study base will be all subjects (≥ 18 years of age) recorded in any of the databases during the study period (see [Section 7.2.2.2](#)) with at least one year of valid data and having a recorded HF diagnosis and a statin prescription.

7.2.2.2 Study period

The study period starts at the launch date of LCZ696 in the countries of interest (see (planned) launch dates in [Table 7-1](#) below).

[figure not shown]
Table 7-1 LCZ696 (Entresto®) launch date in the countries of interest

Country	Launch date
Denmark	December 2015
Italy	April 2016
Netherlands	July 2016
Spain	October 2016
United Kingdom	December 2015

The period over which information is retrieved for each subject may start before the launch date. The study period ends for each reporting at the date that the databases will download their data for the study (see [Table 7-5](#)) or when the practices last supplied the data, which will allow for the use of the most updated data.

A graphical display of the design including information on start of study period, follow-up of subjects in the study base and end of study etc. can be found below in [Figure 7-1](#).

Figure 7-1 Graphical display of the study design

FU = follow-up; HF = heart failure

7.2.2.3 Start and end of follow-up

Follow-up for each subject in the study base will start at the latest of the following points in time:

- Start date of LCZ696 launch
- Reaching age 18 years
- Having at least one year of valid data in the database (to allow for assessment of co-morbidities)

Follow-up ends at the earliest of the following dates:

- Last data download in practice
- Date that the patient transfers out of the database
- Date of death

7.2.2.4 Case-control sample

7.2.2.4.1 Inclusion

Within the population base (see above, [Section 7.2.2.1](#)), all subjects with a new (first-time) episode of myotoxicity (and separately, all cases of hepatotoxicity, or with acute pancreatitis) that occur during follow-up will be identified ([Section 7.2.2.3](#)).

To qualify as a case, patients need to have (i) a HF diagnosis before the event, (ii) have current statin exposure at the index date (= recorded date of the outcome of interest). These

cases will be matched to all potentially available control patients (i.e. study base subjects without the outcome of interest at the index date of the case and still in follow-up) from the same data source and who also have a HF diagnosis together with current statin exposure at the corresponding index date. Controls will be matched to cases on age (year of birth), sex and index date. Controls will have the same calendar date as index date as their matched case.

The incidence density sampling will be done separately for all three outcomes of interest, i.e. separately for myotoxicity, hepatotoxicity, or acute pancreatitis.

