7.4 Data sources

This study will be conducted by using five European databases that comprise routine health care data. This will provide a reflection of real-world circumstances and prescribing behaviors. The databases have been selected based on their geographic location, the availability of population-based data on drugs, plus their recognized reputation in the area of drug utilization and safety research. Multiple countries are included in order to provide international data and to guarantee sufficient exposure to LCZ696.

The data for this study will be retrieved from The Clinical Practice Research Datalink (CPRD) from the UK and will be used through a Novartis license, the Sistema d'Informació per al Desenvolupament de la Investigació en Atenció Primària' (SIDIAP) from Spain provided by IDIAP Jordi Gol, the Health Search CSD Longitudinal Patient Database (HSD) from Italy provided by Società Italiana di Medicina Generale, the PHARMO Database Network (PHARMO) from the Netherlands provided by the PHARMO Institute for Drug Outcomes Research, and the Aarhus University Prescription Database from Denmark provided by Aarhus University.

All analyses will be performed in collaboration between [REDACTED], the scientific lead, and [REDACTED], the coordinating centre for the study according to contractual agreements.

Table 7-5 provides an overview of database characteristics including the available data. These databases have a mean follow-up ranging from 2.5 to 11 years. The databases are representative of the country-specific populations in terms of age and gender. The databases that will be used are primary care databases (except for the Aarhus database from Denmark and PHARMO from the Netherlands) and available data are complete as they come from the general practitioners' [GPs] electronic primary care records. The primary care databases represent 3-20% of the country specific total population. The total number of persons in the source population encompassing all five databases will be around 16 million in 2016.

Table 7-5 Overview of databases to be used for the study

Characteristic	Database				
	PHARMO	CPRD	Aarhus	HSD	SIDIAP
Country	Netherlands	United Kingdom	Denmark	Italy	Spain
Type of database	EMR	EMR	ADM	EMR	EMR
Number of patients, millions	1.2*	5.7 (approx. 55% linked to HES data)	1.8	1.5	5.1 (1.7 linked to hospital data)
Date in	Yes	Yes	Yes	Yes	Yes

Characteristic	PHARMO	CPRD	Database		
			Aarhus	HSD	SIDIAP
Date out	Yes	Yes	Yes	Yes	Yes

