7.4.1 Clinical Practice Research Database (CPRD) – UK

The CPRD; from the UK collates the computerized medical records of general practitioners (GPs) in the UK who act as the gatekeepers of healthcare and maintain patients' life-long electronic health records. As such they are responsible for primary healthcare and specialist referrals, and they also store information stemming from specialist referrals, and hospitalizations. The data recorded in the CPRD include demographic information, prescription details, clinical events, preventive care, specialist referrals, hospital admissions, and major outcomes, including death. The majority of the data are coded in READ Codes

(Booth 1994); however, additional text data is also available, which can improve the sensitivity and specificity of data. Validation of data with original records (specialist letters) is also available.

Importantly, CPRD operates a careful and continual quality control procedure that ensures that only practices that are “up-to-standard” (UPS) are included in the research dataset. The dataset is generalizable to the UK population based upon age, sex, socioeconomic class and national geographic coverage.

There are currently approximately 13.2 million patients (acceptable for research purposes) – of which 5.7 million are active (still alive and registered with the GP practice) – in approximately 680 practices. Data include demographics, all GP/healthcare professional consultations (phone, letter, email, in surgery, at home), diagnoses and symptoms, laboratory test results, treatments, including all prescriptions, all data referrals to other care, hospital discharge summary (date and ICD code), hospital clinic summary, preventive treatment and immunizations, death (date and cause). For a proportion of the CPRD panel practices (~55%), the GPs have agreed to permit CPRD to link at patient level to the Hospital Episode Statistics (HES) data.

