The HES is a data warehouse containing details of all admissions to National Health Service (NHS) hospitals in England (~168 acute NHS Trusts) collected by the Health & Social Care Information Centre. HES is the data source for a wide range of healthcare analysis for the NHS, government and many other organizations and individuals. The HES database contains dates of hospital admissions, primary and secondary diagnoses (coded using the ICD-10 classification), and related procedures (coded using the ICD-10 classification and Office of Population Censuses and Surveys Classification of Interventions and Procedures, Fourth Version). Linked data can be analyzed over a period from January 1997 up to the most recent available HES year (1-2 years delay).

CPRD is listed under the ENCePP resources database (www.encepp.eu/encepp/resourcesDatabase.jsp).

7.4.2 Sistema d'Informació per al Desenvolupament de la Investigació en Atenció Primària' (SIDIAP) – Spain

GPs play an essential role in the public health care system of Spain, as they are responsible for primary health care, long-term prescriptions and specialist and hospital referrals. The Spanish public health care system covers more than 98% of the population. The SIDIAP database comprises of electronic medical records of a representative sample of patients attended by GPs in Catalonia (North-East Spain), covering a population of more than 5.1 million patients (about 80% of the total of 7.5 million population of Catalonia) from 274 primary care practices with 3,414 participating GPs. The SIDIAP data comprises the clinical and referral events registered by primary care health professionals (GPs and nurses) and administrative staff in electronic medical records, comprehensive demographic information, prescription and corresponding pharmacy invoicing data, specialist referrals, and primary care laboratory test results. Hospital admissions and their major outcomes can be identified for a number of practices, covering a total 1.7 million active patients. Health professionals gather this information using ICD-10 codes (primary care records) and ICD-9 (hospital admissions), and

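### In SIDIAP, hospital outcomes can be seen only in linked patients, but controls are not matched on linkage; CPRD is affected only if HES is used to find cases

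*Protocol*

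**What the plan says.** Protocol Section 7.2.2.4.1 fixes how controls are chosen. They come "from the same data source and who also have a HF diagnosis together with current statin exposure at the corresponding index date", and "Controls will be matched to cases on age (year of birth), sex and index date". All available controls are taken. Hospital linkage is not a matching factor, and no section restricts to it or stratifies by it.

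The data-source sections describe two databases in which hospital information is not uniform:

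- **SIDIAP (Section 7.4.2):** "Hospital admissions and their major outcomes can be identified for a number of practices, covering a total 1.7 million active patients". Table 7-5 gives 5.1 million patients in all and limits its hospitalization entry to the linked 1.7 million. Tables 7-2 to 7-4 list ICD-9/10 for SIDIAP outcomes, and ICD-9 is its hospital coding, so hospital records are meant to contribute cases.
- **CPRD (Section 7.4.1):** "For a proportion of the CPRD panel practices (~55%), the GPs have agreed to permit CPRD to link at patient level", here to HES. The GPs also hold hospital information themselves: "they also store information stemming from specialist referrals, and hospitalizations". Table 7-5 marks hospitalizations as available without limiting this to linked patients. Tables 7-2 to 7-4 list READ codes only, while Section 7.6 includes the UK among the countries using ICD codes.

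Section 7.9 accepts that outcome misclassification may differ between databases. It argues that within one database it will be alike for a case and its matched controls.

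**The concern.** A control should be a person who would have been found as a case had the event occurred. An unlinked SIDIAP patient whose event is recorded only in hospital cannot be found as a case, but is still eligible as a control for a linked case. The defence in Section 7.9 needs capture to be uniform within a database, and in SIDIAP it is not.

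Linkage is set by practice. If uptake of a newly launched drug also varies by practice or area, linkage is related to both case finding and exposure, and the odds ratio shifts. The direction is unknown. A downward shift would matter most, because the study aims to rule out a 3-fold or 5-fold risk. Covariates first recorded in hospital (surgery, ERCP, some comorbidity) may also be more complete in linked patients, so adjustment could differ in quality between a case and its controls.

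The concern is greatest for acute pancreatitis, acute liver failure and rhabdomyolysis. It is weaker for myalgia, which need not lead to hospital care.

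**Working it through.** **1. The plan's own figures.** Table 7-6 follows from the log-odds-ratio non-inferiority formula with a true odds ratio of 1 and four controls per case:

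n = (1.645 + 0.842)² × (1 + 1/4) / [p(1 − p) × (ln margin)²]

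With p = 20%, a margin of 3 gives 40.02 (stated 40) and a margin of 5 gives 18.65 (stated 19). Linkage does not enter the formula, so the point leaves these numbers as they are.

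**2. Linked shares.** SIDIAP: 1.7/5.1 = 33.3%. CPRD: about 55% of 5.7 million, or 3.1 million.

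**3. Linked share among cases.** Let L be the linked share in the study base, and s1 and s0 the probabilities that an event is found in linked and unlinked patients:

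w = L·s1 / [L·s1 + (1 − L)·s0]

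The protocol gives neither s1 nor s0. Assuming 0.95 and 0.50:

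- SIDIAP: 0.3167 / (0.3167 + 0.3333) = 49% of cases linked, against 33% of controls.
- CPRD, only if HES finds cases and these values apply: 0.5225 / (0.5225 + 0.2250) = 70%, against 55%.

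**4. Effect on a true odds ratio of 1.** With LCZ696 use pL in linked and pU in unlinked patients (assumed), exposure is w·pL + (1 − w)·pU in cases and L·pL + (1 − L)·pU in controls. For SIDIAP with 15% v 5%, cases have 0.4872 × 0.15 + 0.5128 × 0.05 = 9.87% and controls 8.33%. The odds ratio is 0.1095/0.0909 = 1.20.

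| LCZ696 use, linked v unlinked (assumed) | SIDIAP | CPRD, if HES finds cases |
|---|---|---|
| equal | 1.00 | 1.00 |
| 12% v 8% | 1.07 | 1.07 |
| 15% v 5% | 1.20 | 1.16 |
| 8% v 12% | 0.94 | 0.93 |
| 5% v 15% | 0.85 | 0.83 |

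**5. Other assumptions.** With only 30% capture in unlinked SIDIAP patients and use of 15% v 5%, the odds ratio is 1.38. A second parameterisation sets overall use at 20% and lets 25% to 100% of events be visible only through linkage. For SIDIAP it gives 1.02 to 1.20 if use is 1.25 times higher in linked patients, 1.06 to 1.71 if twice as high, and 0.95 to 0.55 if half as high. With use unrelated to linkage it is 1.00 throughout.

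**6. After matching on linkage.** Cases and controls in a set then have the same linkage status. The difference between w and L disappears and the odds ratio in step 4 returns to 1.00.

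**The case against.** Several counter-arguments have force.

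- **CPRD.** A reader might infer from the 55% figure that hospital outcomes are invisible in the other 45%. The protocol does not support that: GP records hold hospitalization information and discharge summaries, and the outcome tables name READ codes only. Section 7.4.1 also puts HES one to two years behind, so late index dates may lack HES data even in linked patients. If unlinked capture were 85%, use of 15% v 5% would move the CPRD odds ratio only to 1.03. This objection stands, and it makes the CPRD part conditional.
- **Same study base.** A reader might infer that cases and controls come from different populations. They do not: database, index date and eligibility criteria are shared. What differs within that base is how completely events are found.
- **Bias is not shown.** Exposure is read from prescription or dispensing files, not from hospital linkage. Incomplete case finding unrelated to exposure leaves the odds ratio unbiased, and no section says that LCZ696 use varies with linkage. This stands; the figures above are illustrations.
- **Dilution and margin.** The results are for single databases and are pooled over five, three of which do not have this partial linkage. With 40 cases and 20% use, the standard error of the log odds ratio is √(1.25/6.4) = 0.44. The one-sided 95% upper limit is then exp(1.645 × 0.44), or about 2.07 times the estimate. Even an odds ratio of 1.20 gives about 2.5, below 3.
- **The SAP.** Stratification or a linked-only sensitivity analysis could be placed there. That is true, but the matching rule and the Section 7.9 argument are fixed in the protocol, and the argument is wrong for SIDIAP.

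**Conclusion.** The point holds for SIDIAP. Hospital-recorded outcomes are identifiable in one third of its patients, the matching rule ignores this, and linked patients will be over-represented among cases of mainly hospital-treated outcomes. The Section 7.9 statement does not hold within that database. For CPRD the point applies only as far as HES is used to find outcomes, which the protocol leaves open.

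Whether the odds ratio is biased is not established. It requires LCZ696 use to differ by linkage, or covariates to be captured unevenly. Under the assumed 95% v 50% capture, a true SIDIAP odds ratio of 1 would read about 1.07 to 1.20, or 0.94 to 0.85 with the pattern reversed, and 1.00 if use is unrelated to linkage. This is a worthwhile, inexpensive improvement. It does not show that the study would reach a wrong conclusion.

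**What to change.** - In Section 7.2.2.4.1, add hospital-linkage status at the index date as a matching factor for SIDIAP, or stratify the analysis by it.
- State whether HES is used to find CPRD outcomes, and bring Tables 7-2 to 7-4 and Section 7.6 into line. If it is used, apply the same factor to CPRD, counting a patient as linked only where HES coverage reaches the index date.
- Correct Section 7.9 to say that capture can differ within a database by linkage, and that matching or stratification deals with this.

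The cost is one more variable in the extraction and some loss of eligible controls. That loss should be small, because all available controls are taken and the power calculation needs only four per case. No cases need be dropped for lack of linkage, and Table 7-6 stays as it is. Restricting the main analysis to linked patients would cost far more: if applied to both databases, the source population in Table 7-5 would fall from 15.3 million to about 9.3 million (1.2 + 3.1 + 1.8 + 1.5 + 1.7). That option is better kept as a sensitivity analysis.

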7.2.2.4.2 Exclusion

Cases and/or their matched controls who have any of the recorded outcomes of interest will be excluded:

- No recorded heart failure diagnosis at or prior to the index date
- No current or recent use of statins (see [Section 7.3.1](#)) at the index date
- History of the particular event of interest prior to the start of follow-up or during follow-up:
 - For myotoxicity, we will exclude subjects with a history of myotoxicity prior to start of follow-up (both in cases and controls)
 - For hepatotoxicity, we will exclude subjects with a hepatotoxic event prior to start of follow-up (chronic, acute, viral, or drug-induced) (both in cases and controls)
 - For the acute pancreatitis outcome, we will exclude subjects with recorded pancreatitis (acute or chronic, or pancreatic cancer) as well as myotoxicity prior to start of follow-up (as myalgia or rhabdomyolysis have been reported before development of acute pancreatitis [[Jones et al 2015](#)]) (both in cases and controls)

7.3 Variables

7.3.1 Exposures of interest

Drug exposures of primary interest are statins and LCZ696. Information on these variables will be obtained from the prescription/dispensing files (for codes for statins, see Annex 3 Section 12.3.2, [Table 12-1](#)). The duration of each prescription/dispensing will be calculated by dividing the amount by the prescribed dose (if available) and otherwise by the national defined daily dose (DDD) equivalent. Exposure to LCZ696 will be assessed at the index date (date of outcome of interest) and categorized in the following categories of recency of use:

- Current use: the prescription duration covers the index date or stops at most 7 days before
- Recent use: exposure ends between 8 and 90 days before the index date

For current users of LCZ696 at the index date, we will further classify the duration of exposure in the following categories:

- Short: Current use and initiated within past 30 days prior to index date
- Middle: Current use and initiated within past 31-90 days prior to index date
- Long: Current use and initiated more than 90 days prior to index date

For current users of statins, we will look at the daily dose in DDD equivalents for the statin component (see Annex 3, Section 12.3.3, [Table 12-1](#)) of the most recent prescription and categorize as:

- Low (< 1 DDD)
- Medium (1 DDD-1.5 DDD)
- High (> 1.5 DDD)

For the secondary analyses (see [Section 7.7.2.3](#)), the type of statin that is used closest to the index date will determine the type of statin.

Other exposures of interest will be drugs that may confound or modify the potential association; these are listed under the covariates (see [Section 7.3.3](#)). All drugs will be extracted on the basis of their ‘Anatomical Therapeutic Chemical’ (ATC) codes, and durations calculated as described above for the main exposures of interest.

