7.5 Study size/power calculation

The sample size is calculated following a non-inferiority approach (Wang and Chow 2007), with the intent to demonstrate that the increased risk due to LCZ696 exposure is less than 3-fold for hepatotoxicity and less than 5-fold for myotoxicity or acute pancreatitis.

Forty cases with hepatotoxicity will allow ruling out a 3-fold increased risk with a one-sided test (80% power, 5% type I error), assuming a conservative case:control ratio of 1:4 and conservatively, that 20% of the statin-exposed HF patients concomitantly use LCZ696 in the control group (Table 7-6).

Assuming an incidence rate of acute hepatic events in statin-treated HF patients of 6.1 and 12.9/10,000 PYs (Cziraky et al 2006), the underlying study base is expected to be comprised of at least about 66,000 and 31,000 patient-years (PYs), respectively.

A total of 19 cases with a myotoxic event will allow ruling out a 5-fold increased risk (Table 7-6). Assuming IR of myopathy in statin-treated HF patients between 2.3 and 9/10,000 PYs (Macedo et al 2014), the underlying study base should comprise of at least about 83,000 and 21,000 PYs, respectively.

The underlying study base should comprise of at least about 38,000 PYs in order to observe 19 cases of acute pancreatitis assuming an IR of statin-associated acute pancreatitis of 5/10,000 PYs (Kuoppala et al 2015).

Table 7-6 Sample size scenarios for a one-sided non-inferiority test (80% power, 5% type 1 error)

[figure not shown]
Risk to be ruled out	No of cases needed	
	with 10% LCZ696 use	with 20% LCZ696 use
5	33	19
3	71	40

Risk to be ruled out	No of cases needed	
	with 10% LCZ696 use	with 20% LCZ696 use
2	179	100

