7.7.2.3 Primary and secondary analyses

Conditional logistic regression analyses will be used to estimate crude and adjusted relative risks (expressed as odds ratios [ORs]) of each specific outcome with corresponding 95% confidence intervals (CIs).

The primary analysis is current LCZ696 and statin versus current use of statin (any dose) without current use of LCZ696.

Secondary analyses comprise investigation of dose of statin and duration of LJC696, recent use of LJC696 or statins, and individual statins. In the dose specific analysis for statins the reference category will be current low dose of statins and non-use of LJC696.

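### The current-use rule in 7.3.1 does not exclude a prescription dated on the index date, so LCZ696 exposure can be counted more often in cases than in controls and the OR can rise with no true effect

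*Protocol*

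**What the plan says.** Section 7.3.1 fixes when LCZ696 exposure is assessed: "Exposure to LCZ696 will be assessed at the index date (date of outcome of interest"). It then gives the operational rule: "Current use: the prescription duration covers the index date or stops at most 7 days before". Nothing there says when the supply must have begun.

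Section 7.1 words the window differently. Exposure "within a certain risk period prior to the index date (= date of safety event of interest) will be assessed", which points to time before the event.

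The shortest duration class in 7.3.1 is "Short: Current use and initiated within past 30 days prior to index date". The other two classes also count days back from the index date, and none mentions the index date itself.

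Section 7.2.2.4.1 sets the index dates. A case must "have current statin exposure at the index date (= recorded date of the outcome of interest"). For controls: "Controls will have the same calendar date as index date as their matched case".

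The rule feeds the main result. Section 7.7.2.3 states: "The primary analysis is current LCZ696 and statin versus current use of statin (any dose) without current use of LCZ696". Sections 7.2.2.4.2 and 7.3.3.1 refer back to 7.3.1 for statin use and for interacting drugs. The only exposure sensitivity analysis named in 7.7.2.5 concerns missing first prescriptions of LCZ696.

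**The concern.** Read literally, a supply that begins on the index date covers the index date, so the patient is a current user. For a case, that date is by construction a day with a healthcare record, and prescriptions are often written at such contacts. For a matched control it is an arbitrary calendar day. The chance of picking up a new prescription on exactly that day therefore differs by case status for reasons unrelated to any drug effect.

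Two kinds of record change status:

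- LCZ696 is first recorded on the index date. The patient moves from non-user to current user.
- Supply ended more than 7 days earlier and is renewed on the index date. The patient moves from recent or past user to current user.

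A same-day renewal in a continuing user changes nothing.

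At stake are the primary OR and, more sharply in relative terms, the early-exposure OR. If day 0 is read as outside the Short class, these patients are current users with no duration category.

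**Working it through.** **1. The plan's own figure.** Section 7.5 plans "with a one-sided test (80% power, 5% type I error"), with 1:4 matching and 20% LCZ696 use in controls. On the log-OR scale with true OR 1:

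n cases = (1.645 + 0.842)² × (1 + 1/4) / [p(1 − p) × (ln margin)²].

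For p = 0.20 and margin 3: 6.183 × 1.25 / (0.16 × 1.207) = 40.02. The other cells of Table 7-6 come out at 18.65 and 100.53 (20% use) and at 33.15, 71.15 and 178.72 (10% use). The table reproduces.

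**2. Primary OR as a function of the day-0 share.** Let s be the share of otherwise unexposed cases given LCZ696 on the index date, and f the control-to-case ratio of that probability. The protocol gives neither, so both are assumed. With true OR 1 and baseline use p0:

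case prevalence = p0 + (1 − p0)s; control prevalence = p0 + (1 − p0)sf.

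Example: p0 = 0.20, s = 0.02, f = 0. Case prevalence is 0.216, and OR = (0.216/0.784)/(0.20/0.80) = 1.10.

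| Baseline use | s = 0.5% | 1% | 2% | 5% |
|---|---|---|---|---|
| 20% (planned) | 1.03 | 1.05 | 1.10 | 1.26 |
| 10% (also in Table 7-6) | 1.05 | 1.10 | 1.20 | 1.53 |
| 5% (assumed low uptake) | 1.10 | 1.20 | 1.41 | 2.05 |

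The table uses f = 0, the worst case. With f = 0.25 and s = 5% the OR is 1.19 at 20% use and 1.36 at 10%. With f = 1 it is 1.00.

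**3. Primary OR from contact rates.** Assume a = 5% to 10% of patients start LCZ696 per year, c = 6 to 24 contacts per year, and q = 0.25 to 1 as the share of case index dates that are prescribing contacts. Assume also that 3% of patients have lapsed, of whom 30% are renewed at a contact (0.03 × 0.30 = 0.009). Then, at 20% use:

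- case prevalence = 0.20 + qa/c + 0.009q
- control prevalence = 0.20 + a/365 + 0.009c/365

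Low end (a = 0.05, c = 24, q = 0.25): 0.2028 against 0.2007, OR 1.01. High end (a = 0.10, c = 6, q = 1): 0.2257 against 0.2004, OR 1.16. Starts alone at c = 12 give 1.01 to 1.05.

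**4. Short class, reading day 0 as included.** Controls: a × 30/365 + a/365. Cases: a × 30/365 + qa/c. Each is set against non-users at 20% current use.

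Example: a = 0.05, c = 12, q = 0.5. Cases 0.00619 and controls 0.00425; non-users 0.7979 and 0.7999; OR = (0.00619/0.7979)/(0.00425/0.7999) = 1.46. For q = 0.25, 0.5 and 1, c = 12 gives about 1.2, 1.5 and 2.0. At c = 6 the range is about 1.5 to 3.0, and at c = 24 about 1.1 to 1.5. The result barely depends on a.

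**5. How many patients that class would hold.** Without any day-0 addition, its prevalence is a × 30/365 = 0.41% to 0.82%. Forty cases would contain 0.16 to 0.33 expected Short users, and nineteen 0.08 to 0.16.

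**6. Power.** The power is Φ[(ln margin − ln OR)/SE − 1.645], where SE² = 1/[n p1(1 − p1)] + 1/[4n p0(1 − p0)] and p1 is the case prevalence from step 2 (f = 0, 20% use). For 40 cases and margin 3 it is 80.0% at s = 0, 77.6% at 1%, 74.9% at 2% and 66.1% at 5%. For 19 cases and margin 5 it is 80.6%, 79.3%, 77.9% and 73.1%.

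**The case against.** The strongest reply is that the protocol never says day 0 counts. Section 7.1 and all three duration classes look back from the index date, and section 7.7 leaves detail to an SAP that is not to hand. This stands in part: the wordings conflict, and the SAP may settle it. But 7.3.1 already states an operational rule for the primary contrast, and programmed as written that rule admits day 0.

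Second, sections 7.9 and 7.4 indicate that specialist-started LCZ696 may go unrecorded in the UK, Italian and Spanish data until the GP continues it. A first GP record on the index date may then belong to a patient already taking the drug. An apparent lapse may likewise be continuing use where duration is estimated. Both are fair, so a reader should not infer that every index-date exposure is spurious or could not have caused the event. They do not rescue the rule, however: if such users are captured because of the event visit, the capture itself is differential. The statement in 7.9 that this misclassification is likely non-differential would not then hold.

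Third, the mechanism varies. Aarhus records pharmacy refill dates and PHARMO includes out-patient dispensings, and nothing in the protocol shows that a visit for acute pancreatitis or liver failure starts LCZ696 as often as a routine visit does. This stands, and it is why the sizes above are ranges.

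Fourth, an upward bias works against ruling out harm, so it does not create false reassurance, and it is small beside margins of 3 and 5. That is right for the primary OR at the planned uptake.

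**Conclusion.** The point holds as a defect of definition with a one-directional but probably modest effect. As written, 7.3.1 lets index-date prescriptions count, 7.1 suggests otherwise, and the duration classes leave day 0 unplaced. Because cases are anchored to a recorded event and controls are not, the OR can exceed 1 with no true effect.

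At 20% use the primary OR bias is about 1.01 to 1.16 under the assumed rates, or 1.05 to 1.10 if 1% to 2% of otherwise unexposed cases gain day-0 exposure. It is larger at lower uptake, which section 7.9 calls the most important uncertainty. The Short class shows the largest relative bias, about 1.1 to 3.0, but with under one expected exposed case at the planned numbers its OR will be hard to interpret in any event. All contact, start and lapse rates are assumptions; the protocol supplies none.

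A reader might infer that controls cannot acquire exposure on the index date, or that the OR must rise. Neither follows. Controls can have a prescription that day, only less probably, and if the probabilities were equal the bias would vanish. Nor is the sample size in error: Table 7-6 reproduces, and it assumes no such bias.

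**What to change.** Reconcile 7.1 and 7.3.1 in one definition: current use means a prescription or dispensing dated before the index date whose duration covers the index date or ends at most 7 days before it. Apply it identically to cases and controls, and to LCZ696, the duration classes, statin eligibility and comedication.

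Add a sensitivity analysis that counts index-date prescriptions, or uses a short lag before the recorded outcome date, because some first GP records on that day may be specialist-started users who are already exposed.

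The cost is one sentence in the protocol and one inequality in the extraction script. The downside is that those users, and any genuine same-day exposures, are classed as unexposed in the main analysis; the sensitivity analysis shows how much this matters. With no day-0 exposure counted, the expected OR under no effect is 1.00 in this model, power is 80.0% (40 cases, margin 3) and 80.6% (19 cases, margin 5), and the Table 7-6 case numbers stay as they are.
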